Enrollment for protocol 14-AA-0042 was recently completed. This was a single-blind, dose-escalating, placebo-controlled, within-subject study using PF-05190457 (50mg and 100mg b.i.d.) or matched placebo in non-treatment seeking heavy drinking subjects (n = 12 completers). At each visit, subjects received the study drug on Day 1 (twice), Day 2 (twice) and then in the morning of Day 3 (drug dosing phase), after which an alcohol session (drug/alcohol interaction session) was conducted, followed by repeated clinical and research assessments and repeated blood sampling for the PK/PD outcomes. Across the three drug conditions (placebo, PF-05190457 50 mg b.i.d., PF-05190457 100 mg b.i.d.), there were no serious adverse events and the drug was well-tolerated, as patients reached the targeted dose per study design, and none dropped due to study drug-related side effects was reported. During the drug/alcohol interaction session, there were no statistically significant differences in adverse events nor on alcohol-related biphasic effects (sedation and stimulation). During the drug dosing phase, there were no statistical differences in adverse events between the three drug conditions. Analysis of Day 1 EKG vs. Day 3 EKG showed a significant difference in the QTc interval in the two drug conditions vs. placebo; however, this statistically significant difference did not have a clinical significance given that all QTc values always remained within the normal range. Additionally, the statistical significance was mainly driven by a decrease in the QTc interval from Day 1 to Day 3 in the placebo condition. Nonetheless, out of an abundance of caution, the present protocol will have specific safeguards, as detailed in the exclusion criteria and in the criteria for participant withdrawal.

While Protocol 14-AA-0042 was primarily designed as a Phase 1b drug/alcohol interaction study, we also took the advantage of having research participants at the NIH CRC in order to conduct preliminary assessments of the potential role of PF-05190457 on alcohol craving. The main goal of these preliminary assessments was to provide information that may better guide the present protocol. In particular, we found the following:

- 1. PF-05190457 did not reduce alcohol craving assessed during drug dosing in the hospital room**
- 2. PF-05190457 reduced alcohol priming-elicited craving (Figure 4).**

[figure not shown]

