f) Smoking. The high co-morbidity between alcohol and nicotine dependence reflects a strong connection between alcoholism and smoking (Littleton et al., 2007). We will assess the severity of nicotine dependence with the Fagerström Test for Nicotine Dependence (FTND; Heatherton et al., 1991), cigarettes smoked before and then during the duration of the study (via the TLFB) and Breath CO levels, for possible exploratory analyses, which might guide future alcohol/smoking studies. At the NIH Clinical Research Center, inpatients can smoke in a specific smoking area whose access is controlled by our nursing staff. Therefore, we will be able to collect the precise number of cigarettes smoked during the inpatient stay. Furthermore, when experimental procedures will take place, smoking breaks will be standardized across and between subjects. Finally, during each Stage, we will perform a smoking topography procedure to assess smoking behaviors such as smoking intensity (e.g., number of puffs, inter-puff intervals, peak puff velocity), while subjects smoke their first cigarette of the day on specified days during the study in the NIH CRC smoking area – this will help us to pilot a smoking topography device that we have recently purchased and would like to use in future studies.

g) Genetics. A single whole blood sample (~2 mL) from each subject will be shipped to [name] from URI where it will be stored and DNA analyzed for polymorphisms of genes involved in PF-05190457 metabolism and transport, alcohol metabolism and ghrelin activity.

6. Nutrition

Participants will receive standardized meals developed in collaboration with the NIH Nutrition Department to control and monitor caloric intake within and across participants. Food-related data, including % of meal eaten, will be recorded. Participants may receive a regular diet during the washout period.

7. Study Medication Check

There is a possibility that subjects and/or Investigators might identify if they received the PF-05190457 compound or placebo. Therefore, at the end of each Stage, we will ask subjects and study physician which they believed they received. This information will be recorded.

8. Measurements for safety monitoring

The following safety measures will be performed repeatedly as per below (and also as needed, as the clinical situation dictates):

- Vital signs, weight and BrAC (every day during each Stage, prior to study drug administration)

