- Check for potential adverse events (every day during each Stage)
- Blood glucose via finger stick (3 times during each Stage)
- Stanford Sleepiness Scale (3 times during each Stage)
- EKG, electrolytes and liver and kidney function tests: at the beginning of Stage 1 before administration of the study drug and again at the end of Stage 1, and then twice during Stage 2 (before first drug administration and at the end of Stage 2)

9. Additional Considerations

Medication Dose Justification. The dose of 100 mg b.i.d. was the highest dose used in the previous study (14-AA-0042) and was the dose that led to a reduction in cue-induced craving (Figure 5), the primary aim for this study. The same dose of 100 mg b.i.d. was previously used in the last Phase I study (B3301002; clinicaltrials.gov: NCT01372163) conducted by the manufacturer (Pfizer).

Medication Compliance. During the study, the drug will be administered at the NIH Clinical Center, which will assure 100% compliance with the study medication.

Missing data. While missing data will be minimized, we do expect that we will not always be able to collect all planned data (an example of a scenario is missing blood samples due to problems with the cannula, hemolysis, and other technical problems). Nonetheless, every effort is made to minimize these unforeseen problems with equipment or study procedures. If one should occur, we will ask the participant to repeat a specific experimental procedure (if allowed by the overall study schedule, if it is feasible and if the participant agrees) in order to avoid having to discard other usable data from a participant. Subjects may receive additional compensation if experimental sessions are repeated, consistent with the NIDA/NIAAA Remuneration Policy.

Data sharing with other protocols. Data obtained under this protocol and the NIAAA screening 14-AA-0181 protocol as well as with Protocol 14-AA-0066, Behavioral and Functional MRI Task Development, Implementation and Testing may be shared and combined for analysis. Both protocols, 14-AA-0181 and 14-AA-0066 protocols are protected by a Certificate of Confidentiality. This will also allow to avoid repeating assessments that are scheduled in both protocols during the same period of time, therefore avoiding duplication and minimizing participants' fatigue.

This protocol does not meet criteria for genomic data sharing.

OUTPATIENT PHASE

11. Follow-up Visits and Behavioral Intervention

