Less common side-effects are: abdominal discomfort, abdominal distention, abdominal pain, upset stomach, diarrhea, constipation, defecation urgency, gastrointestinal sounds abnormal, flatulence, gastroenteritis, upper respiratory tract infection, nasal congestion, nasopharyngitis, rhinorrhea, oral herpes, elevated transaminases, rhabdomyolysis, arthralgia, pain, pain in extremity, pain in jaw, swelling, hot flush, conjunctival hyperemia, acne cystic, face edema, hemoglobin decreased, dizziness, paraesthesia, hypoaesthesia, lethargy, dermatitis contact, photosensitivity reaction, hematoma, hemorrhage, abnormal eye exam, muscular weakness, musculoskeletal chest pain, depressive mood, euphoria, drowsiness, increased appetite, insomnia, irritability, difficulties to concentrate and sweating.

Most of the side-effects were mild and a few of them were moderate. There were no severe side-effects.

Our team in the CPN lab as well as the CC nursing staff are well familiar with PF-05190457, as we have already conducted and successfully and safely completed another study with this drug (14-AA-0042). Risks of medication will be minimized through careful and detailed screening of participants to minimize recruitment of those who might be at higher risk for adverse events, as well as careful and detailed monitoring of adverse events and participant well-being during the study. As detailed in the research strategy, a screening visit will be performed before enrolling any subject, under the NIAAA Screening Protocol 14-AA-0181. This screening visit will include a comprehensive clinical assessment, including physical exam, testing, psychiatric and medical history, blood and urine tests, and interviews aimed at assessing all

inclusionary/exclusionary criteria listed. For enrolled subjects, adverse medication effects will be systematically evaluated and recorded. *Ad hoc* clinical, laboratory and diagnostic assessments may be performed, should a participant present with specific symptoms, as the clinical situation may dictate. If adverse events are serious or intolerable, participants will be withdrawn from the study and given treatment and or referral as the situation dictates. Concomitant medications will be evaluated carefully before randomizing participants, as detailed in the exclusion criteria section above.

Blood draw and finger stick

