Blood Clinical: serum electrolytes, AST, ALT, GGT, bilirubin, Creatinine

▲IVETU Questionnaires:

Perceived Family History: weight and alcohol problems

Implicit Theories of Weight, Alcohol Use and Eating

Causal Beliefs Scale for Alcohol Dependence and Casual Beliefs Scale for Body Weight

Perceptions of Personal Control and Treatment Control

Self-Stigma and Alcohol Dependence

Perceptions of passing down propensity for disease

▲Including Post-IVETU Questionnaires:

Thoughts about the Buffet Scenario

Environmental Presence

Post-IVETU Symptom Checklist

Real-world Food Behavior

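### Rhabdomyolysis is a listed side effect but no scheduled test names creatine kinase, so symptomless muscle injury, or an AST rise read as hepatic, is left to clinical judgement

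*Combined protocol and SAP*

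**What the plan says.** **Side effects.** Section K (Study Drug) includes, among the less common effects, "oral herpes, elevated transaminases, rhabdomyolysis, arthralgia, pain, pain in extremity, pain in jaw" and later "abnormal eye exam, muscular weakness, musculoskeletal chest pain". It attributes the list to the manufacturer's studies and to the previous study, 14-AA-0042. It gives no rates and concludes: "There were no severe side-effects". Section C says of 14-AA-0042 that "there were no serious adverse events and the drug was well-tolerated".

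**Scheduled laboratory tests.** Section E, item 8 sets "EKG, electrolytes and liver and kidney function tests: at the beginning of Stage 1 before administration of the study drug", with repeats at the end of Stage 1 and at the start and end of Stage 2. Appendix 2 itemises the panel: "Blood Clinical: serum electrolytes, AST, ALT, GGT, bilirubin, Creatinine". Section M.5 gives the DSMB the same tests plus finger-stick glucose. It presents these as parameters that are included, not as a closed list, and puts adverse events first. Section G.1 also describes the clinical samples, by example only. CK is named in none of these four places, nor elsewhere in the text supplied.

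**Safeguards.** Section E, item 8 has a daily adverse event check in each Stage and opens: "The following safety measures will be performed repeatedly as per below (and also as needed, as the clinical situation dictates". Section K says that ad hoc "clinical, laboratory and diagnostic assessments may be performed, should a participant present with specific symptoms, as the clinical situation may dictate". Section M.3a allows discretionary withdrawal for clinically significant laboratory changes.

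**The concern.** The protocol gives its other prominent expected effects a scheduled measure that bears on them directly. Rhabdomyolysis has only indirect markers (AST, creatinine, electrolytes), and AST is hard to read in this trial. Section F excludes AST or ALT only above three times the upper normal limit, so a participant may enter with a raised value. Transaminase rises are themselves a listed drug effect. A rise that came from muscle could therefore be put down to the liver.

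What is at stake is participant safety: an injury that causes no complaint could pass unrecognised in the person who has it. No estimate or test in the efficacy analysis depends on it.

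**Working it through.** The plan states no figure on this point, so the check compares the side-effect list with the schedule and then counts draws.

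**1. Listed effect against scheduled measure** (Section K against Section E, item 8)

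| Listed effect | Scheduled measure |
|---|---|
| Somnolence | Sleepiness scale, 3 times per Stage |
| Lower glucose | Finger stick, 3 times per Stage |
| Raised heart rate | Daily vital signs |
| Elevated transaminases | AST and ALT, 4 draws |
| Rhabdomyolysis | No specific test; AST, creatinine and electrolytes at the same 4 draws |

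**2. How a muscle injury would come to light**

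- With symptoms: the daily check finds pain or weakness in an inpatient, ad hoc tests follow, and the event reaches the DSMB through the adverse event item in Section M.5. This route is covered.
- Without symptoms, but with a change in AST, creatinine or electrolytes: the scheduled draw can show it. No text requires such a change to lead to a CK test; that is left to the clinician.
- Without symptoms and without a prompting change: no scheduled test is aimed at it.
- Timing: draws fall only at the start and end of a Stage that may last up to 14 days. After the end-of-Stage 2 draw this protocol schedules no further clinical laboratory test. The outpatient visits are optional, and the clinical checks listed for them are breath alcohol, vital signs and weight.

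**3. Draws** (Section E inpatient overview and item 8; Section H.3)

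- Scheduled clinical draws per participant: 2 Stages × 2 = 4.
- One Stage is active and one is placebo, so draws at the end of active dosing: 1 of 4 = 25%.
- Planned completers: 1 × 41 = 41. Upper bound, if everyone enrolled completes the active Stage: 1 × 55 = 55.
- Of these, scheduled to include CK: 0.
- In participants who take the drug first, the Stage 2 pre-dose draw also follows active dosing, after a washout that may be as short as 2 days.

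**4. Room for extra withdrawals** (Section H.3)

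- Expected completers: 55 × (1 − 0.25) = 41.25, against 41 needed. The margin is 41.25 − 41 = 0.25.
- One further lost completer gives 41.25 − 1 = 40.25, below 41.
- Appendix 2 puts Cue Reactivity last among the tasks and the closing assessments on the following day. On that schedule a raised CK at the end-of-Stage 2 draw comes after the primary outcome has been collected, so only the other three draws could cost a completer.

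**The case against.** The case against raising this is substantial. The side-effect list gives no rates and no attribution, and it also contains items such as oral herpes and cystic acne. It reads more like a pooled event list than a set of established drug effects. None was severe. Participants are inpatients who are asked about adverse events daily. CK is unnamed but not excluded. Participants are also enrolled in 14-AA-0181 (Section I.7), whose data may be combined with this study's so that assessments are not duplicated (Section E, item 9). Its laboratory list is not among the documents, so it may already supply CK. Finally, counting draws without CK restates the omission and does not measure harm.

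All of this stands, and it is why the point is optional. It does not remove the difficulty of reading AST in this population, nor the dependence on clinical judgement when there are no symptoms.

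A reader might go further and infer three things that the documents do not support:

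- *That nothing in the protocol could lead to a CK test.* Section E, item 8 and Section M.3a both leave room for clinical discretion, and Section K provides for ad hoc tests.
- *That the DSMB would be blind to rhabdomyolysis.* Any detected event reaches it as an adverse event. Failure to reach the DSMB is only failure to detect, not a second gap.
- *That a number of missed cases can be projected.* No rate is given from which to project one.

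**Conclusion.** The point holds as a small, optional safety improvement. A listed effect has no scheduled test of its own, and the remaining gap is muscle injury that is silent or is mistaken for a hepatic AST rise. Its size can be stated only as draws: one per participant at the end of active dosing, 41 as planned and at most 55. The conclusion rests on two assumptions: that 14-AA-0181 does not already measure CK during the stay, and that Appendix 2 is the working definition of the panel, since it is more specific than the examples in Section G.1. The primary analysis and the power calculation do not depend on it.

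**What to change.** First check whether 14-AA-0181 supplies CK during the inpatient stay. If it does not:

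- Add CK to Blood Clinical at the four existing draws (Section E, item 8 and Appendix 2) and to the blood tests in Section M.5.
- Use the Stage 1 pre-dose value as baseline. Read the Stage 2 pre-dose value mainly as a check for an unresolved rise, because it may follow active drug after a short washout.
- State that a raised value leads to a repeat test and clinical review against baseline, with withdrawal under Section M.3a only if the change is judged clinically significant.

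The cost is a short amendment and one assay on blood already drawn, with no new scheduled visit, staff or procedure; a raised value would add a repeat sample. The downsides are incidental rises to interpret and a small risk of extra withdrawals when the completer margin is 0.25. The repeat-and-review step is there to limit that risk.

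The cover page records that the IND was withdrawn in August 2021, and the documents do not say whether dosing had ended. If it had, the change belongs in any later trial of this compound.

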11.1 Measures (see also Appendix)

Motivation: The Stages of Change Readiness and Treatment Eagerness Scale (SOCRATES) (Miller and Tonigan, 1996) measures whether or not patients recognize drinking problems, ambivalence or uncertainty about drinking, and whether or not the patient is currently taking steps to change. It is a measure of overall motivation for abstaining from alcohol. Situational Motivation Scale (SIMS) (Guay et al., 2000): evaluates the specific type of motivation prompting behavioral change – it differentiates between four different types of motivation: intrinsic, identified regulation, external regulation, and amotivation. The questionnaire uses the following definitions of each motivational type:

- Intrinsic motivation: behaviors that are engaged in for their own sake, in other words, for the pleasure and satisfaction derived from performing them.
- Identified regulation: behaviors the patient recognizes as beneficial, but ones that she pursues because of its perceived outcome, rather than because she finds the behaviors inherently satisfying
- External regulation: behavior patients feel forced into because it regulates rewards or helps them avoid negative consequences
- Amotivation: behaviors pursued with no sense of purpose or expectation of rewards

Insight: The Hanil Alcohol Insight Scale (HAIS) (Kim et al., 1998) is a well validated, 20-item questionnaire used to objectively evaluate a patient’s insight into their alcoholism. Reflective Functioning: Beck Cognitive Insight Scale (modified) (Beck et al., 2004) measures “cognitive insight,” or a person’s capacity to achieve insight into a specific problem or issue. The 15 item scale evaluates capacity for insight through questions that reflect a patient’s self-certainty and self-reflectiveness and we have modified this scale to focus on alcohol use. The Mindful Attention Awareness Scale (Brown and Ryan, 2003) is a 15 item scale that measures dispositional mindfulness and the Curiosity and Exploration Inventory-II (Kashdan et al., 2009) is a 10 item scale that measures the tendency to seek and embrace new knowledge and experiences. The University Rhode Island Change Assessment Scale (URICA) (DiClemente & Hughes, 1990) is a 32-item self-report measure that includes 4 subscales measuring the stages of change with respect to treatment for substance use disorders: Precontemplation, Contemplation, Action, and Maintenance.

Shift in attributions question (modified from Schechter et al. (2006)) measures shifts in attitudes toward alcohol: *“Tell me 5 words or short phrases (adjectives) that describe how you think alcohol affects you.”*

We hypothesize that video feedback in conjunction with motivational interviewing and self-modeling, then, has the potential to help patients to shift motivations and behaviors towards alcohol, as well as maintain abstinence or reduce alcohol drinking, over time.

11.2 Overview of the Procedure

During this outpatient phase, patients will come into the NIAAA Outpatient Clinic at the NIH Clinical Center for 8 visits and there will be two phases: 4 visits of motivational interviewing sessions with video feedback and 4 visits of supportive counseling, using a crossover design with the order of the two phases counterbalanced across participants. All counseling sessions will be conducted by a physician, nurse practitioner, nurse or masters level counselor.

Motivational Interviewing with Video feedback Phase

Motivational interviewing sessions will be conducted at the initial visit and at alternating visits thereafter with video feedback of these sessions during the intervening weeks. During the videotaped motivational interviewing session, the patient and clinician will discuss in progression the following topics:

- Reasons for abstinence
- Triggers and the patient's reactions (physical, mental) to them
- Reasons for abstinence having just discussed their triggers
- Description of a time when the patient refused alcohol
- Reasons for abstinence having just discussed a time when they had successfully refused alcohol

We start the conversation with a discussion about the reasons for abstinence to gain insight into why they want to stop drinking prior to making them conscious of how they react to alcohol and how they have tried to avoid it in the present or the past. The second portion of the discussion is a dialogue about the patient's triggers and responses to them. We included this question to instigate a conversation that will help us understand how a patient's motivation shifts when presented with triggers. Following a conversation about the triggers, we return to a discussion about the patient's motivation for abstinence. We chose to include a discussion about a patient's drive to abstain from alcohol after discussing triggers to see whether or not conversations about experiences with alcohol, or people and objects that remind them of alcohol, causes any variation in the way patients discuss their motivation. The fourth portion of our conversation on motivation for abstinence will discuss how patients have successfully coped with triggers and situations where alcohol was present. This portion of the conversation serves two purposes: to help patients understand how pre-existing and developed behaviors have laid the foundation for successful abstinence, and to give them a chance to reflect on the experience of refusing alcohol. Lastly, we end with a discussion of a patient's motivation for abstinence, to evaluate the impact discussions of successful abstinence when faced with alcohol or alcohol-related stimuli may have on a patient's reasons for motivation or self-reported motivation levels. The session should take 30-45 minutes to complete. Between video-taping and motivational interviewing sessions, the clinician will review the video-tape for clips that represent positive motivations, negative motivations, strong reactions to triggers, and opportunities to present models of successful behavior for the patient to try and emulate.

Visits 1 and 3: At Visit 1, the subject will complete the following questionnaires at baseline:

- Motivation to change (SOCRATES) (Miller & Tonigan, 1996)
- Situational Motivation Scale (SIMS) (Guay et al., 2000)
- Hanil Alcohol Insight Scale (HAIS) (Kim et al., 1998)
- Beck Cognitive Insight Scale (Beck et al., 2004), modified
- Attributions towards alcohol (modified WMCI question) (Schechter et al., 2006)
- Mindful Attention Awareness Scale (Brown and Ryan, 2003)
- Curiosity and Exploration Inventory-II (Kashdan et al., 2009)
- University Rhode Island Change Assessment Scale (URICA) (DiClemente & Hughes, 1990)
- Meta-cognition tasks: Meta-cognition, an individual's ability to comprehend and be mindful of their thought process, is thought to be disrupted in individuals that abuse substances (Goldstein et al., 2009). One task will measure an individual's sense of agency (the amount an individual feels they are the cause of actions around them).

The other task will measure individual's perceptual meta-cognition abilities, or how well they believe they can discriminate between two stimuli.

1. Agency Task: The agency task was designed to assess individual's sense of control (Metcalf et al., 2007). Individuals will use a computer mouse to "catch" falling stimuli (Xs or Os) that are randomly distributed across the screen by moving a small box across a horizontal track. Individuals will then be assessed on their subjective feelings of control over the small box and performance on the task. Turbulence of the mouse, speed of the scroll, and density of targeted stimuli will vary across the 24 trials conducted. This allows us to collect both subjective (self-reported control and performance) and objective (turbulence of the mouse and actual performance) to compare an individual's ability to think about their performance and agency.
2. Flemings Dots Task: The Fleming Dots task was developed to assess perceptive meta-cognition. Two circles will appear on the computer screen containing varied number of dots. After the two circles disappear, individuals undergo a forced choice paradigm, in which they choose the circle that contained the most dots. The difference in dots between the two circles is titrated so that after two continuous correct answers the difference in the number of dots between the two circles decreases, and after one incorrect answer the difference in the number of dots increases. This is done so that the difficulty of the task is equal between participants (Fleming et al., 2010). Individuals are then asked to rate how confident they feel about their answer.

Then the patient will undergo a motivational interviewing session as described above. For Visit 3, a videotaped motivational interviewing session only will be done.

Visits 2 and 4: During these visits, the patient will view the video of the previous week's videotaped session. Clinicians who run motivational interviewing video feedback sessions with patients should pre-select four thirty second clips to highlight while the patient and clinician watch the entire video clip from the previous week. The clinician should select video clips that represent the following:

- An "optimal" moment – a moment when the clinician believes the patient discusses their reasons for motivation most authentically.
- A moment of stress – a moment when the patient demonstrated a stress or emotional reaction to discussions of triggers or encounters with alcohol
- A moment of successful coping – a moment when the patient discusses successful restraint in using alcohol when presented with triggers or situations related to alcohol.
- A "suboptimal" moment – a moment where the clinician believes the patient's reasons for abstinence sound superficial and disingenuous.

We have chosen to identify optimal, stressful, successful coping, and suboptimal moments because previous studies have shown the importance of making patients aware of the thought processes and patterns that make them susceptible to relapse. Allsop & Saunders (1991) demonstrated that "the processes involved in relapse are identical to those involved in the making and breaking of any resolution to change any behavior". Thus, the optimal moment and moment of successful coping help the patient recognize the appropriate attitudes and decision making processes that will help them abstain from alcohol over time. Identifying the moments of stress and disingenuous reasons for motivation, likewise, increase awareness of situations and thought processes that may make the patient more prone to relapse. These feedback sessions will also be videotaped.

The videotapes will also be coded for verbal and nonverbal behavior with respect to motivation for change. A Reliance Agreement has been put in place with Montclair State University, where AI [name] will assist in developing a rating for

assessing the videotaped motivational interviewing sessions and feedback sessions that will be coded for verbal and nonverbal behavior with respect to motivation for change.

After the feedback session, patients will fill out the following questionnaires to assess changes in motivation, insight, cognitive insight, and attributions towards alcohol at intervals throughout the experiment: SOCRATES, SIMS, HAIS, modified Beck Cognitive Insight Scale (modified), the modified WMCI question, the Mindful Attention Awareness Scale, the Curiosity and Exploration Inventory-II, the URICA and Metacognition Tasks: Agency Task and the Flemings Dots Task.

Supportive Counseling Phase

The 4 visits of supportive therapy will consist of outpatient visits with supportive counseling sessions lasting approximately the same duration as the motivational interviewing sessions. In addition, the questionnaires: SOCRATES, SIMS, HAIS, modified Beck Cognitive Insight Scale, Mindful Attention Awareness Scale, the Curiosity and Exploration Inventory-II, URICA and the Meta-cognition tasks: Agency Task and Flemings Dots Task will be completed after sessions on Visits 2 and 4 of this phase.

F. Inclusion and Exclusion Criteria

a. Description of study population

This study will enroll individuals with AUD who are treatment- or non-treatment-seeking. The following inclusion/exclusion criteria will be assessed via the NIAAA Screening Protocol 14-AA-0181:

b. Inclusion criteria

1. Male or female individuals 18-70 years old (inclusive)
2. Current Alcohol Use Disorder (AUD) by DSM-5 criteria based on the SCID
3. Most recent urine drug test for illegal drugs of abuse is negative
4. Most recent Clinical Institute Withdrawal Assessment for Alcohol – revised (CIWA-Ar) score is ≤ 8
5. Heart rate ≤ 100 on two separate measurements, both assessed after CIWA-Ar score is ≤ 8
6. Female subjects must be of non-childbearing potential as defined by at least one of the following criteria:

a) Females 45 –70 years old, who are menopausal, defined as follow:

i) Females who are between 45 – 55 years old: they will be considered menopausal if they satisfy all the following three requirements during screening: 1) they are in amenorrhea, defined as absence of menstruation for the previous 12 months; 2) they have a negative urine pregnancy test; and 3) they have a serum FSH level within the laboratory’s reference range for postmenopausal females.

ii) Females who are between 56 – 70 years old: they will be considered menopausal if they are in amenorrhea, defined as absence of menstruation for the previous 12 months before screening.

OR

b) Females 21-70 years old, who have a documented hysterectomy and/or bilateral oophorectomy.

All other female subjects (including females with tubal ligations and females that do NOT have a documented hysterectomy) will be considered to be of childbearing potential.

7. Male subjects must use one of the following methods of contraception from the first dose of study medication and until 28 days after dosing (given that it is unknown whether the effects of this drug can cause birth defects):

a. Abstinence.

b. A condom AND one of the following:

- Vasectomy for more than 6 months.
- Female partner who meets one of the following conditions:
 - a) Has had a tubal ligation, hysterectomy, or bilateral oophorectomy;
 - b) Is post-menopausal;
 - c) Uses one of the following forms of contraception:
 - Copper or hormonal containing IUD;
 - Spermicidal foam/gel/film/cream/suppository;
 - Diaphragm with spermicide;
 - Oral contraceptive;
 - Injectable progesterone;
 - Subdermal implant.

c. **Exclusion criteria**

1. Lifetime clinical diagnosis of schizophrenia or bipolar disorder

2. EKG with QTc > 450 msec as determined by the Fridericia formula

3. BMI < 18.5 kg/m² or anorexia

4. BMI ≥ 40 kg/m²

5. History of epilepsy and/or seizures

NOTE: individuals who have a history of alcohol withdrawal seizures may be in the study as long as they have been abstinent from alcohol for at least 2 weeks prior to consent and during that period of abstinence, there were no seizure episodes (otherwise, participant remains not eligible).

6. Most recent blood tests show creatinine ≥ 2 mg/dL, AST or ALT > 3x the upper normal limit, hemoglobin <10.5 g/dl

7. Subjects who have diabetes and/or are treated with any drug with glucose lowering properties such as sulfonylurea, insulin, metformin, thiazolidinediones (TZD), Dipeptidyl peptidase-4 (DPP4) inhibitors, or Glucagon-like peptide-1(GLP-1)agonists (due to the glucose-lowering properties of PF-05190457 observed in healthy volunteers)

8. Exclusionary Medications:

A.

Naltrexone, acamprosate, alcohol dehydrogenase inhibitors, topiramate, gabapentin, ondansetron, benzodiazepines, and alpha-1 blockers, baclofen, drugs that are known to prolong the QTc interval and barbiturates

as well as hormone replacement therapy; medications and dietary/herbal supplements (like St. John's wort) that interact with Cytochrome P450 3A4. Patients who take these medications may be enrolled in the study only if the potentially interacting medication has been stopped for a period of at least 5 half-lives of the interacting medication before PF-05190457 administration. Patients who take these medications on an as needed (PRN) schedule or take the medication as a one-time dose as part of a medical procedure or a diagnostic test, for example, may not have to wait the 5 half-lives' period of time before enrollment; this will be evaluated on a case by case basis by the MAI and/or PI, based on the specific pharmacological properties of the medication.

9. Unable to pass a finger rub hearing test
10. Vision is unable to be corrected to (Snellen) 20/100
11. Clinically-significant history of motion or car sickness, or history of vestibular disorders
12. Any other reason or clinical condition for which the PI or the MAI will consider unsafe for a possible participant to participate in this study

Exclusion Criteria for fMRI only:

1. Have contraindications for brain fMRI, as determined by the NIAAA MRI Safety screening form (conducted under the 14-AA-0181 Screening Protocol)
2. Colorblindness (this would prevent subject from completing the Stroop task) using the Ishihara Test for Color Deficiency, Concise Edition, 2014.

G. Collection and Storage of Human Specimens or Data

1. Use of samples

Blood samples will be used for:

- a) Pharmacokinetic use: samples will be used to analyze PF-05190457 plasma concentrations, its known metabolites, and conduct PK/PD analyses (analyses conducted at [name] URI Lab) as per fully executed MTA.
- b) Research use: samples will be used for future analyses (performed either in our own lab at NIH or at [name] URI Lab) of blood ghrelin levels, as well as other feeding-related peptides (e.g., leptin, GLP-1, amylin, GIP, pancreatic polypeptide, PYY, GH, insulin, etc.), stress-related hormones (e.g., ACTH, cortisol, etc.) and/or inflammatory markers (e.g., cytokines, etc.) that may be analyzed for exploratory analyses.
- c) Clinical use: samples will be used to analyze clinical labs via the NIH Clinical Center Department of Laboratory Medicine (e.g., glucose, AST, ALT, GGT, bilirubin, Creatinine, and electrolytes).

2. Sample Storage

Data will be stored on NIH data servers, under the management of the ORIT, NIAAA and under the management of the NIDA IRP Biomedical Informatics Section (BIS). The existence and types of information contained in the data management system have been publicly reported as required by the FOIA.

Blood not processed via the Department of Laboratory Medicine at the Clinical Center will be processed and stored in -80 °C freezers. All biological specimens obtained under this protocol will be stored in coded form (protocol plus subject number) in freezers located in the access-controlled laboratory area of NIDA. Additional samples will be shipped to URI, [name] lab. All results generated in [name] lab for this project will be sent to the PI and his team at NIH.

Storage of video tapes: Video tapes will be stored on a password protected computer operated by an approved research team member under supervision of the PI. A copy of videotapes will be sent to [name] registered email address through NIH secure email file transfer. All tape recordings and copies made that are collected under this protocol will be destroyed no later than 1 year following study completion.

Biosensor Data

Data from biosensors will be sent electronically to [name] laboratory at MIT where it will be analyzed.

Data being analyzed will be identified by participant codes and identifying information will be removed. Each participant will be assigned a participant code and their data will be associated with this code number. The participant code only will be attached to data transferred to MIT using the NIH Secure Email File Transfer (SEFT) approved encryption service. All data with identifying information will be stored on password-protected computers in the CPN Section at NIAAA.

Bed Sensor: Although the device is capable of streaming data wirelessly over Bluetooth to a tablet or mobile phone, for this study, the data shall be recorded internally on a memory card. (Micro-SD). The data will be copied to a laptop at NIAAA and data will be transferred to MIT for data analysis.

Thermal Camera: images will be downloaded from the iPad to an NIAAA computer will be transferred electronically to MIT for analysis.

H. **Statistical Analysis**

1. Analysis of data/ study outcomes

